3 INTRODUCTION

Dry eye disease (DED) is a multifactorial disease of the ocular surface characterized by a loss of homeostasis of the tear film, and accompanied by ocular symptoms, in which tear film instability and hyperosmolarity, ocular surface inflammation and damage, and neuronal sensory abnormalities play etiological roles ([Craig et al, 2017](#)). DEWS II hypothesizes that dry eye disease (DED) is "...initiated by desiccating stress and perpetuated by a Vicious Circle of ocular surface inflammation (Bron et al, 2017)." Thus, no matter what initiates a patient's dry eye disease (e.g., allergic eye disease, topical preservative toxicity, or xerophthalmia) all patients eventually enter a chain of inflammatory events that perpetuate the disease.

Experimentally, the expression of IL-1, TNF- α , and IL-6 by ocular surface epithelia are critical to the ocular surface dry eye inflammatory response. A key step in the amplification process for inflammation is the generation of signals that recruit inflammatory cells to the site of inflammation: 1) chemokines and 2) integrin adhesion molecules. Chemokines produced at the ocular surface (e.g., CCL3, CCL4, CCL5, CXCL9, CXCL10, and CX3CL1) can bind macrophages, dendritic cells, neutrophils, and activated T cells. The other key step in homing inflammatory cells to the ocular surface is the expression of endothelial integrin adhesion molecules (e.g., ICAM-1, VCAM-1). ICAM-1 and VCAM-1 are adhesion molecules that bind to inflammatory cells expressing the ligand, integrated leukocyte function antigen 1 (LFA-1; integrin α L β 2) and very late antigen 4 (VLA-4; integrin α 4 β 1), respectively. Integrins facilitate cell-cell and cell-extracellular matrix (ECM) adhesion and include the β 1, β 2, β 4, immunoglobulin, and selectin super families. Known targets for treating ocular inflammation include α L β 2 and α 4 β 1 (Bron et al, 2017).

Lifitegrast ophthalmic solution (Xiidra®) 5% was approved by the US FDA for the treatment of DED in 2016. Lifitegrast is an antagonist of LFA-1 (also known as CD11a/CD18 or α L β 2). Lifitegrast demonstrated a statistically significant treatment response in the objective endpoint, change from baseline to Day 84 in inferior corneal staining score in the Phase 2 and OPUS 1 studies and a statically significant treatment response in the subjective endpoint, change from baseline to Day 84 in eye dryness score (VAS) in the OPUS 2 and 3 studies ([Semba & Gadek, 2016](#)).

Natalizumab, an antibody directed against the α 4- integrin subunit, has been shown to profoundly inhibit inflammation and improve clinical outcomes in both multiple sclerosis and Crohn's disease. Topical, ocular application of BIO-8809 (Anti-VLA-4 small molecule) decreased corneal fluorescein staining, conjunctival T-cell infiltrates, and TNF α expression in cornea and conjunctiva in a murine dry eye model ([Ecoiffier et al, 2008](#)).

AXR-159 (GW559090) is potent and selective antagonist for the α 4 subunit, α 4 β 1 and α 4 β 7 integrins, which has been formulated as an eye drop and has been shown to be safe and well tolerated in the eye with no target organ toxicity identified at doses up to 30 mg/kg/day in animal models. It lacks significant systemic exposure following topical ocular administration due to low systemic exposure and its high clearance rate from the circulation.

In preclinical murine models of DED, AXR-159A improved corneal staining with similar efficacy and onset of action, as the topical steroid dexamethasone. Topical steroids are an unapproved, but effective treatment for DED and often serve as positive controls in preclinical models of DED. Topical ophthalmic corticosteroids are commonly used for the treatment of dry eye disease (DED) (Holland et al, 2007; DEWS, 2007; Avunduk et al, 2003; Pflugfelder et al, 1999; Pflugfelder et al, 2004; Yang et al, 2006). Topical AXR-159A also significantly reduced corneal uptake of Oregon Green Dextran (OGD) compared to vehicle-treated disease controls, murine model of dry eye, in a dose-dependent manner (1, 3, 10, and 30 mg/mL) with 30 mg/mL showing the greatest reduction in OGD staining. When administered topically, corneal expression of IL-1 α , matrix metalloproteinase (MMP)-9, chemokine ligand 9 (CXCL9), and TGF- β 1 were reduced in AXR-159A -treated eyes. Topical treatment with AXR-159A decreased dendritic cell activation in lymph nodes. The effects on corneal staining and cellular composition in draining cervical lymph nodes (CLN) were not reproduced by systemic administration of AXR-159A, suggestive of a local role for integrin antagonism in the treatment of dry eye (Krauss et al, 2015).

The presence of CD4+ T cells at the ocular surface in DED and the successful treatment of ocular surface inflammation with cyclosporine (i.e., Restasis® and Ikervis®) suggest that adaptive immunity is important in the pathophysiology of DED. Initiation of an adaptive immune response requires that antigens at the site of inflammation are presented by professional antigen presenting cells that migrate to regional lymphoid tissue to activate and expand antigen-specific T cells. The ability of AXR-159A to decreased dendritic cell activation in lymph nodes suggests it has the ability to block adaptive immunity associated with DED.

Given the above clinical experience in man with an antibody directed against the α 4-integrin subunit and preclinical work with novel α 4 integrin antagonists, i.e., AXR-159A and BIO-8809, in pre-clinical models of DED, AxeroVision Inc. believes that AXR-159 has potential as a novel agent for the treatment of dry eye disease.

4 STUDY OBJECTIVES

TABLE 4-1 TABLE OF OBJECTIVES, ENDPOINT, AND ENDPOINT JUSTIFICATION

OBJECTIVES	ENDPOINTS	JUSTIFICATION FOR ENDPOINTS
Primary		
Stage 1: To evaluate the safety, tolerability, and exploratory pharmacodynamics of up to 2 different concentrations of AXR-159 Ophthalmic Solution (30 mg/mL or 50 mg/mL) dosed three-times daily (TID) or twice-daily (BID) for up to 12 weeks compared to its vehicle in patients with Dry Eye Disease (DED).	
Adverse Events:
 
Incidence rates of each treatment-emergent adverse event summarized by primary system organ class and preferred term.Tables for all treatment-emergent adverse events regardless of causality.Tables for all treatment-emergent adverse events considered to be treatment-related.Shift tables for safety variables (e.g., IOP, biomicroscopy, and ophthalmoscopy). 
Signal of Efficacy:
 
Change from Baseline in inferior corneal staining score in the study eyeChange from Baseline in total corneal staining score in the study eyeChange from Baseline in eye dryness measured using a visual analogue scale (VAS)Change from Baseline in Total Ocular Surface Disease Index (OSDI) score	
The endpoints for safety and tolerability are all commonly used in drug trials.
 
The efficacy endpoints match those captured in the Xiidra clinical development program and are listed on the U.S. Food & Drug Administration webpage (https://www.accessdata.fda.gov/drugsatfda_docs/nda/2016/208073Orig1s000TOC.cfm).

Stage 2: To evaluate the safety, tolerability, and pharmacodynamics of up to 3 different concentrations of	See Above for Stage 1	See Above for Stage 1

OBJECTIVES	ENDPOINTS	JUSTIFICATION FOR ENDPOINTS
AXR-159 Ophthalmic Solution (3 mg/mL, 30 mg/mL or 50 mg/mL) dosed three-times daily (TID) or twice-daily (BID) for up to 12 weeks compared to its vehicle in patients with Dry Eye Disease (DED).		
Secondary		
See Above for Stages 1 & 2	
• Schirmer's test w/o anesthesia• Tear film break-up time (TBUT)• Conjunctival redness score• Sodium fluorescein corneal staining• Lissamine green conjunctival staining• Ocular Discomfort Score• Patient symptoms (visual analog scale [VAS])• OSDI (subscale and items)• Symptom Assessment in Dry Eye (SANDE)• Proportion of patients with a TBUT \geq 10 seconds at each visit• Proportion of patients with a Schirmer's test \geq 10 mm at each visit• Proportion of patients with a Total OSDI $<$ 18 at each visit• Proportion of patients with an Ocular Discomfort Score = 0 at each visit• Tear collection (for exploratory analyses) (selected sites)	See Above for Stages 1 & 2

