15 APPENDICES

APPENDIX 1: SCHEDULE OF VISITS AND MEASUREMENTS

Procedure	Visit 1 Day -14±2		Visit 2 Day 1	Visit 3 Day 15±2	Visit 4 Day 43± 2	Visit 5 Day 85 ± 2	
	Pre CAE®	Post CAE®				Non CAE®	Post CAE®
Informed Consent / HIPAA	X						
Medical / Medication History and Demographics	X						
Medical / Medication Update			X	X	X	X	
Vehicle Run-in Collection			X				
Study Drug Collection			X	X	X	X	
Review of Qualification Criteria	X	X	X				
Adverse Event Query		X	X	X	X	X	X
Pregnancy Test	X ^a					X ^a	
Visual Analog Scale	X	X	X	X	X	X	X
Ora Calibra® Ocular Discomfort Scale	X	X	X	X	X	X	X
SANDE Questionnaire	X		X	X	X	X	
OSDI® Questionnaire	X		X	X	X	X	
Visual Acuity (ETDRS)	X		X	X	X	X	
Vital Signs	X		X			X	
Bulbar Conjunctival Hyperemia	X	X	X	X	X	X	X
Slit-lamp Biomicroscopy	X	X	X	X	X	X	X
Tear Collection (Selected Sites)			X			X	
Oculus Keratograph 5®	X ^b		X ^b	X ^b	X ^b	X ^b	
TFBUT	X	X	X	X	X	X	X
Fluorescein Staining (Ora & Oxford Scales)	X	X	X	X	X	X	X
Lissamine Green Staining (Oxford Scale)	X	X	X	X	X	X	X
15 Minute Wait Period	X		X	X	X	X	
Schirmer's Test	X		X	X	X	X	
CAE® Exposure	X					X	
Discomfort Grading during CAE® Exposure	X					X	
Intraocular Pressure		X	X	X	X		X
Ophthalmoscopy Exam		X ^c					X ^c
CBC and Differential Blood Draw		X					X
Pharmacokinetic Blood Draw			X ^d		X ^d		
Randomization			X				
Vehicle Run-In Dispensation		X					
Vehicle Run-In Instillation		X					
Study Drug Dispensation			X	X	X		
Study Drug Instillation			X	X	X		X

Procedure	Visit 1 Day -14±2		Visit 2 Day 1	Visit 3 Day 15± 2	Visit 4 Day 43± 2	Visit 5 Day 85 ± 2	
	Pre CAE®	Post CAE®	Non CAE®	Non CAE®	Non CAE®	Pre CAE®	Post CAE®
Ora Calibra® Drop Comfort Assessment			X		X		X
Exit Subject from Study							X

^a To women of child-bearing potential, as defined.

^b TFBUT and Tear meniscus height only; only at selected sites

^c Ophthalmoscopy examination will be dilated at randomization and undilated for Visit 5 unless dilation is necessary

^d Blood samples for pharmacokinetic analysis will only be collected for Stage 1, the first 40 patients in the expansion cohort as follows: Visit 2: pre-dose, Visit 4: pre-dose, 15 min, 30 min, 60 min, 90 min, and 3 hr, & 6 hr post dose.

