16.5 Intraocular Pressure (IOP)

IOP will be measured in each eye by contact tonometry by the examiner and the results will be recorded in mmHg at all scheduled visits, and potentially at an Early Termination Visit. Assessments at Visits 1 and 5 will be post-CAE®. A single measurement is made to obtain a determination of IOP. The same tonometer employing the investigator's standard technique will be used throughout the study. In addition, all reasonable efforts will be made to have the same examiner obtain all IOP measurements for a given subject.

The IOP values and changes from baseline for each eye (study eye and fellow eye) will be summarized using continuous descriptive statistics by visit and eye for each treatment group and for all actively treated subjects. A subject listing of IOP will also be produced.

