16.6 Ophthalmoscopy

Dilated fundus exams will be performed at Visit 1 using indirect ophthalmoscopy. At Visit 5, undilated fundus exams will be performed unless dilation is necessary. The investigator will make observations of the vitreous, retina, macula, choroid and optic nerve.

Observations will be graded as Normal or Abnormal. Abnormal findings that are clinically significant (as determined by the investigator that may interfere with study parameters or otherwise confound the data)

and those that are not clinically significant will be described. An indirect Fundoscopy examination should be performed if retinal disease is detected.

The results will be summarized using counts and percentages for each treatment group at each visit for each eye (study eye and fellow eye). Percentages will be based on the number of subjects in each treatment group with responses. Shift tables for the fundoscopy parameters will also be provided comparing Visit 5 to baseline (Visit 1). A subject listing of the fundoscopy parameters will also be produced.

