16.10 Urine Pregnancy Test

A urine pregnancy test will be conducted for females of childbearing potential at Visit 1 (Day -14 ± 2), Visit 5 (Day 85 ± 2), and may be conducted at an Unscheduled Visit. A listing of urine pregnancy test results will be generated.

17. Interim Analyses

An interim analysis will be performed when the last enrolled patient in Stage 1 completes Month 3 of the Expansion Cohort. There is no plan to stop the study for efficacy on the basis of the interim analysis. However, termination in individual dose groups due to safety, tolerability and/or futility may occur. Statistical significance will not be declared at the time of the interim analysis.

Given the exploratory nature of the study no Type I error adjustments will be made for the interim analysis including the Stage 1 data only.

18. Changes from Protocol-Stated Analyses

There are no changes from the protocol-stated analyses.

19. Revision History

The following revisions were made to SAP Version 2.0.

SAP Section	Revision	Rationale
12.1	Revised compliance calculation to use date of completion/discontinuation rather than date of last in-office instillation	Conservative estimation of compliance for discontinued subjects

12.2	Revised exposure calculation to use date of completion/discontinuation rather than date of last in-office instillation	Conservative estimation of exposure for discontinued subjects
13.1.1	Revised specification of random number seeds for MCMC	Consistency with 13.1.2
13.1.3, 13.1.4, 13.1.5	Revised specification of random number seeds for MCMC	Correction of seed specification

20. Tables

Tables that will be included in the topline delivery are shown in boldface font. Tables that will be included in the interim analysis are qualified as “Stage 1”.

Table Number	Title	Population
TABLE 14.1.1.1	SUBJECT DISPOSITION – STAGE 1	ALL RANDOMIZED SUBJECTS
TABLE 14.1.1.2	SUBJECT DISPOSITION – STAGE 2	ALL RANDOMIZED SUBJECTS
TABLE 14.1.1.3	SUBJECT DISPOSITION – COMBINED STAGE 1 AND STAGE 2	ALL RANDOMIZED SUBJECTS
TABLE 14.1.2.1.1	DEMOGRAPHICS – STAGE 1	MITT POPULATION
TABLE 14.1.2.1.2	DEMOGRAPHICS – STAGE 1	MITT2 POPULATION
TABLE 14.1.2.1.3	DEMOGRAPHICS – STAGE 1	SAFETY POPULATION
TABLE 14.1.2.2.1	DEMOGRAPHICS – STAGE 2	MITT POPULATION
TABLE 14.1.2.2.2	DEMOGRAPHICS – STAGE 2	MITT2 POPULATION
TABLE 14.1.2.2.3	DEMOGRAPHICS – STAGE 2	SAFETY POPULATION
TABLE 14.1.2.3.1	DEMOGRAPHICS – COMBINED STAGE 1 AND STAGE 2	MITT POPULATION

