TABLE 14.3.2.3	ORA CALIBRA® DROP COMFORT SCALE – COMBINED STAGE 1 AND STAGE 2	SAFETY POPULATION
TABLE 14.3.3.1	ORA CALIBRA® DROP COMFORT QUESTIONNAIRE – STAGE 1	SAFETY POPULATION
TABLE 14.3.3.2	ORA CALIBRA® DROP COMFORT QUESTIONNAIRE – STAGE 2	SAFETY POPULATION
TABLE 14.3.3.3	ORA CALIBRA® DROP COMFORT QUESTIONNAIRE – COMBINED STAGE 1 AND STAGE 2	SAFETY POPULATION
TABLE 14.3.4.1	BEST-CORRECTED VISUAL ACUITY (BCVA; LOGMAR) – STAGE 1	SAFETY POPULATION
TABLE 14.3.4.2	BEST-CORRECTED VISUAL ACUITY (BCVA; LOGMAR) – STAGE 2	SAFETY POPULATION
TABLE 14.3.4.3	BEST-CORRECTED VISUAL ACUITY (BCVA; LOGMAR) – COMBINED STAGE 1 AND STAGE 2	SAFETY POPULATION
TABLE 14.3.5.1.1	SLIT-LAMP BIOMICROSCOPY – STAGE 1	SAFETY POPULATION
TABLE 14.3.5.1.2	SLIT-LAMP BIOMICROSCOPY – STAGE 2	SAFETY POPULATION
TABLE 14.3.5.1.3	SLIT-LAMP BIOMICROSCOPY – COMBINED STAGE 1 AND STAGE 2	SAFETY POPULATION

Table Number	Title	Population
TABLE 14.3.5.2.1	SHIFT IN SLIT-LAMP BIOMICROSCOPY – STAGE 1	SAFETY POPULATION
TABLE 14.3.5.2.2	SHIFT IN SLIT-LAMP BIOMICROSCOPY – STAGE 2	SAFETY POPULATION
TABLE 14.3.5.2.3	SHIFT IN SLIT-LAMP BIOMICROSCOPY – COMBINED STAGE 1 AND STAGE 2	SAFETY POPULATION
TABLE 14.3.6.1	INTRAOCULAR PRESSURE (IOP; MMHG) – STAGE 1	SAFETY POPULATION
TABLE 14.3.6.2	INTRAOCULAR PRESSURE (IOP; MMHG) – STAGE 2	SAFETY POPULATION
TABLE 14.3.6.3	INTRAOCULAR PRESSURE (IOP; MMHG) – COMBINED STAGE 1 AND STAGE 2	SAFETY POPULATION
TABLE 14.3.7.1.1	OPHTHALMOSCOPY – STAGE 1	SAFETY POPULATION
TABLE 14.3.7.1.2	OPHTHALMOSCOPY – STAGE 2	SAFETY POPULATION
TABLE 14.3.7.1.3	OPHTHALMOSCOPY – COMBINED STAGE 1 AND STAGE 2	SAFETY POPULATION
TABLE 14.3.7.2.1	SHIFT IN OPHTHALMOSCOPY – STAGE 1	SAFETY POPULATION
TABLE 14.3.7.2.2	SHIFT IN OPHTHALMOSCOPY – STAGE 2	SAFETY POPULATION
TABLE 14.3.7.2.3	SHIFT IN OPHTHALMOSCOPY – COMBINED STAGE 1 AND STAGE 2	SAFETY POPULATION
TABLE 14.3.8.1	VITAL SIGNS – STAGE 1	SAFETY POPULATION
TABLE 14.3.8.2	VITAL SIGNS – STAGE 2	SAFETY POPULATION
TABLE 14.3.8.3	VITAL SIGNS – COMBINED STAGE 1 AND STAGE 2	SAFETY POPULATION
TABLE 14.3.9.1	LABORATORY TESTS – STAGE 1	SAFETY POPULATION
TABLE 14.3.9.2	LABORATORY TESTS – STAGE 2	SAFETY POPULATION
TABLE 14.3.9.3	LABORATORY TESTS – COMBINED STAGE 1 AND STAGE 2	SAFETY POPULATION
TABLE 14.3.10.1	COMPLIANCE WITH STUDY DRUG – STAGE 1	SAFETY POPULATION
TABLE 14.3.10.2	COMPLIANCE WITH STUDY DRUG – STAGE 2	SAFETY POPULATION
TABLE 14.3.10.3	COMPLIANCE WITH STUDY DRUG – COMBINED STAGE 1 AND STAGE 2	SAFETY POPULATION

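### The IOP shift table named in the protocol is left out of the SAP without being declared, and the ophthalmoscopy shift table may mix dilated and undilated exams without labels

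*Protocol*

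**What the plan says.** **Protocol.** Table 4-1 (section 4) places "Shift tables for safety variables (e.g., IOP, biomicroscopy, and ophthalmoscopy" among the adverse-event endpoints of the Stage 1 primary objective, and Stage 2 refers back to the same list.

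**SAP, IOP.** Section 16.5 states: "The IOP values and changes from baseline for each eye (study eye and fellow eye) will be summarized using continuous descriptive statistics". This is done by visit and arm, with a listing by subject. In the table list (SAP section 20), IOP has one family, which begins with "INTRAOCULAR PRESSURE (IOP; MMHG) – STAGE 1" and continues with Stage 2 and the combined stages.

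**SAP, ophthalmoscopy.** Section 16.6 has the Visit 1 fundus exam done with dilation and then says: "At Visit 5, undilated fundus exams will be performed unless dilation is necessary". The same section adds: "Shift tables for the fundoscopy parameters will also be provided comparing Visit 5 to baseline (Visit 1".

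**Schedule.** Footnote c, in protocol Appendix 1 and again in SAP section 3.2, reads: "Ophthalmoscopy examination will be dilated at randomization and undilated for Visit 5 unless dilation is necessary".

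**Departures from the protocol.** SAP section 18 states: "There are no changes from the protocol-stated analyses". SAP section 1 gives the SAP precedence over the protocol on statistical methods, so an analysis missing from the SAP is not planned.

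**The concern.** Safety is a primary objective, and the synopsis describes the trial as the first use of this integrin antagonist as an eye drop in humans. Stage 1 safety results also inform the Data Review Committee's recommendation on Stage 2 and its dose groups (protocol sections 6.1 and 6.3), and the SAP's Stage 1 tables are the interim outputs.

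Two parts of that evidence do not line up. The IOP shift table is named in the protocol, is absent from the SAP, and is not declared as a change. Without it, the reader gets averages and extremes of IOP but no count of eyes that moved into a higher category, by arm. The ophthalmoscopy shift table is planned, but its two columns come from exams that by default use different techniques. A shift in that table can reflect the eye or the way it was examined, and nothing planned tells the two apart.

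**Working it through.** The point is mainly textual, and the plan states no figure to reproduce.

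**Step 1. The three named measures against the SAP table list (SAP section 20).**

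| Measure named in Table 4-1 | Summary tables | Shift tables |
|---|---|---|
| Biomicroscopy | 14.3.5.1.1 to 14.3.5.1.3 | 14.3.5.2.1 to 14.3.5.2.3 |
| IOP | 14.3.6.1 to 14.3.6.3 | none |
| Ophthalmoscopy | 14.3.7.1.1 to 14.3.7.1.3 | 14.3.7.2.1 to 14.3.7.2.3 |

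Two of the three have a shift family of three tables each. The IOP gap is therefore three tables. That IOP is continuous does not explain it: SAP section 16.8 puts blood pressure and pulse, also continuous, into low, normal and high categories.

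**Step 2. What the planned IOP tables can show.** SAP section 8.4 defines a continuous summary as n, mean, SD, median, minimum and maximum. Section 16.5 gives this for the value and the change, by visit, for study and fellow eye separately. These figures do not determine how many eyes crossed a limit.

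An illustration, with a rise and counts that are assumptions and not in the documents: if k study eyes out of n each rise by r, the mean change moves by k × r / n. Take r = 10 mmHg and n = 43 to 53, the expected Stage 1 active group (protocol section 12.1).
- k = 1: 10/53 = 0.19 to 10/43 = 0.23 mmHg.
- k = 3: 30/53 = 0.57 to 30/43 = 0.70 mmHg.

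If no other eye rises further, the maximum change is 10 mmHg in both cases. The table shows that at least one eye rose that far, but not whether it was one or three. The listing would show all of them, without a tabulated count by arm. The conclusion does not depend on these numbers.

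**Step 3. What the ophthalmoscopy shift table compares.** SAP section 16.6 and protocol Appendix 2 give:
- Visit 1: dilated.
- Visit 5: undilated, with dilation where needed. No criterion for need is given.

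The table can therefore hold two kinds of eye: dilated at both visits, and dilated at Visit 1 only. Neither document says that dilation status is recorded or that the table is split by it. On the assumption that an undilated exam shows less of the fundus, a new finding may go unseen and a baseline abnormality may appear resolved. The documents give no rate for either.

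**Step 4. When the dilated exam takes place.** Footnote c puts it at randomization, which is Visit 2. The schedule grid marks ophthalmoscopy only at Visits 1 and 5. Protocol section 10.3.1.1 lists it, with the dilating drug, at Visit 1, and section 10.3.1.2 lists none at Visit 2. Protocol Appendix 2 and SAP section 16.6 also name Visit 1. The footnote and these passages conflict.

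**The case against.** The strongest reply is that individual cases are covered elsewhere. Protocol section 11.1 and SAP section 16.1 require a clinical finding that worsens to a relevant degree to be recorded as an adverse event. Ocular treatment-emergent events are then counted by arm, by preferred term, by maximal severity, and for study and fellow eyes separately. IOP minimum, maximum and listing are planned, and the Data Review Committee meets at least monthly (protocol section 13.7.6). All of this stands. What it does not supply is a count against limits fixed in advance, because adverse-event reporting depends on what each investigator judges relevant.

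Second, Table 4-1 gives its measures as examples, two of the three are delivered, and the SAP supersedes the protocol. That makes the IOP gap modest. It does not make the statement in SAP section 18 accurate, since IOP is named explicitly.

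Third, on the fundus exam, dilation remains possible at Visit 5, an indirect exam is called for if retinal disease is detected, and the same rule applies in all masked arms. This also stands. It leaves lower sensitivity in every arm, with no built-in difference between arms. The exception adds to the labelling problem, because it is what lets the two exam types mix.

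**Conclusion.** The point holds in two limited parts.

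- **IOP.** A shift table named under the primary safety objective is not planned, and the SAP says nothing changed. The size is three missing tables, and the loss is the number and proportion of eyes crossing a category, by arm. This assumes that tables 14.3.6.1 to 14.3.6.3 contain what section 16.5 describes and no more.
- **Ophthalmoscopy.** The shift table may combine like and unlike exams without saying so, and it is less sensitive to new findings in all arms. The size cannot be derived from the documents. This assumes that dilation status is not already captured on a case report form that is not part of them.

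Three stronger readings are tempting and not supported:
- That harm in individual eyes would be missed. Adverse-event tables, the maximum and the listing all remain.
- That a patient who leaves early with raised IOP would appear only in a listing. SAP section 16.5 allows for an Early Termination reading, and protocol section 7.5 has sites try to complete exit procedures. The documents do not say how such readings are tabulated, so this is unspecified and not shown to be a loss.
- That the fundus table is biased between arms, or that baseline findings will appear to resolve. The rule is common to all arms, and the documents support only that they may.

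**What to change.** 1. **SAP section 16.5 and the table list.** Add IOP shift or threshold tables for Stage 1, Stage 2 and combined, by eye and arm, from baseline to each visit and to the worst post-baseline value. State that Early Termination and unscheduled readings count towards the worst value. The sponsor should fix the categories before unmasking. If the tables are not added, declare the omission and its reason in SAP section 18.
2. **SAP section 16.6.** Record at Visit 5 whether each eye was dilated. Present the fundus shift table by exam type, or limit it to eyes examined the same way at both visits and list the rest.
3. **Footnote c** (protocol Appendix 1 and SAP section 3.2). Reconcile it with the schedule grid, protocol sections 10.3.1.1 and 10.3.1.2, protocol Appendix 2 and SAP section 16.6.

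The cost is a few extra tables and one case report form field. None of this requires changing how either exam is done.
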